8.3 Lost to Follow Up

A participant will be considered lost to follow-up if he or she fails to return for 1 scheduled visits and is unable to be contacted by the study site staff. Every reasonable effort will be made to contact these patients to ensure they are receiving appropriate follow up care with documentation of any serious adverse effects (SAEs), adverse effects (AE) or changes in medical condition (for example, Mayo score), diagnoses or medications.

The following actions must be taken if a participant fails to return to the clinic for a required study visit:

- The site will attempt to contact the participant and reschedule the missed visit within 1 week and counsel the participant on the importance of maintaining the assigned visit schedule and ascertain if the participant wishes to and/or should continue in the study.
- Before a participant is deemed lost to follow-up, the investigator or designee will make every effort to regain contact with the participant (where possible, 3 telephone calls and, if necessary, a certified letter to the participant's last known mailing address or local equivalent

methods). These contact attempts should be documented in the participant's medical record or study file.

- Should the participant continue to be unreachable, he or she will be considered to have withdrawn from the study with a primary reason of lost to follow-up.

9. Correlative/Special Studies

9.1 Laboratory Correlative Studies

9.1.1 Microbiome – Laboratory Correlative Study #1

9.1.1.1 *Collection of Specimen(s): Fecal*

9.1.1.2 *Handling of Specimen(s): Frozen -80C*

9.1.2 Lamina propria cells – Laboratory Correlative Study #2

9.1.2.1 *Collection of Specimen(s): Biopsy*

9.1.2.2 *Handling of Specimen(s): Collected in PBS, Processed in [name] lab*

9.1.3 Peripheral Blood – Laboratory Correlative Study #3

9.1.3.1 *Collection of Specimen(s): Blood sample*

9.1.3.2 *Handling of Specimen(s): Processed in [name] lab*

9.2 Special Studies

9.2.1 Special Correlative Study #1

9.2.1.1 Assessment

Microbial alterations, transferability and engraftment will be studied by sequencing DNA material at different timepoints. Previous studies have used reference genome alignments to evaluate microbial engraftment, however this approach does not determine taxonomy at the strain level, and therefore it is less accurate in defining the shared microbes between donor and patient. To overcome this issue metagenomics post-quality control sequences will be profiled using StrainPhlAn pipeline. To determine the degree of the engraftment, we will apply principal coordinates analysis to Bray-curtis distances. Wilcoxon signed-rank (paired) statistical tests will be used to evaluate the level of microbial similarity (Bray-curtis) between donor, pre-FMT and post-FMT. Given the dissimilar microbial composition observed in donor and pre-FMT samples in our preliminary data, we propose to use these microbial signatures to infer the origin of the post-FMT microbes. Briefly, bacteria shared among donor and pre-treatment samples will be removed from the model and the remained unique strains will be calculated. Machine learning models, Random Forest procedure, will be fitted in R-studio to predict bacterial engraftment and their persistence, as previously described.

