3.2 Scientific Rationale for Study Design

The ability to manipulate the human gut microbiome and alter mucosal and systemic immunity remains a central question in the study of IBD. We have previously completed a pilot study for FMT at Weill Cornell and have the clinical research infrastructure and clinical expertise to recruit patients, characterize their response, and complete the data analysis. Work from our lab and others has defined the role for specific bacteria in inducing immune responses in mouse models. We also have defined diagnostic signatures of microbial profiles associated with inflammatory disease phenotype in humans

including rheumatoid arthritis and IBD. Emerging clinical data provides evidence for the clinical efficacy of FMT in patients with ulcerative colitis (UC). Preliminary data from our own research suggests that engraftment and/or particular microbial species correlate with clinical outcome, however the factors that determine microbial engraftment are not well defined. Therefore, we designed a randomized, double-blind, placebo-controlled study to examine the possibility of improving the clinical outcome and microbial engraftment of FMP250 by using prebiotic fiber supplementation in active UC patients. Study subjects will be randomized into three groups: (1) *FMP250+Fiber*, (2) *FMP250-Fiber*, and (3) *PlaceboFMP250 with or without Fiber*. Given that fiber alone has not shown significant benefits previously in many UC studies²⁷, we hypothesize that subjects given *PlaceboFMP250+Fiber* will allow us to assess the placebo rate for FMT (*FMP250only* vs. *PlaceboFMP250+Fiber*). Also, considering that we will utilize single donor FMP250 samples, comparing subjects given *FMP250only* and *FMP250+Fiber* will allow us to scientifically assess primary endpoints of the impact of prebiotic supplement on engraftment and efficacy. *PlaceboFMP250-Fiber* will remove any risk of unblinding and will maintain the integrity of our double blinded study.

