7.1 Study Intervention/Device Description

7.1.1 Investigational and Placebo FMP250

The proposed intervention will deliver 250 milliliters of FMP250 by colonoscopy to the investigational FMP250 treatment groups at day 0. The placebo treatment group will instead receive the placebo FMP250 by colonoscopy at day 0 and then the investigational FMP250 by flexible sigmoidoscopy at week 8.

Investigational FMP250 is biologically active human fecal material that is pre-screened, tested, quarantined, stored, packaged, and labeled by OpenBiome. Placebo FMP250 is a control unit made of glycerol, saline, and food dye that is stored, packaged, and labeled identically to the investigational FMP250, to ensure blinding during delivery. Weill Cornell Medicine has contracted OpenBiome to supply 135 investigational FMP250 and 135 Placebo FMP250 directly to the [name] laboratory at Weill Cornell Medicine over the course of the study.

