FMP250 Inventory Records – Investigator-appointed Weill Cornell research staff will maintain a careful record of the inventory and disposition of all agents received from OpenBiome with the *Material Tracking Log*, an example is pictured below, provided with each shipment by OpenBiome. This form should be kept in a safe space and must be filled out for all units. Once completed, it must be returned to OpenBiome prior to ordering the next shipment.

A	B	C	D	E	F	G	H	I
Item	Unit ID	Expiration Date	Ship Date	Date Received	Frozen on Receipt	Unit Status	Administering Physician	Follow-Up Form Given to Physician
FMP250	0001-0001-01	2/16/15	8/16/14		 Yes  No	 Used  Destroyed		 Yes  No

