7.4.4 Product Labeling and Documentation

OpenBiome's IB indicates that each sample bottle is labeled with (1) the handling and storage warnings, (2) a lot number and (3) the expiration date based on the storage temperature (pictured below from left to right). The lot number is formatted as XXXX-YYYY-ZZ, where XXXX is the donor number, YYYY is the donation number, and ZZ marks the bottle number. Additionally all donor screening results will be provided in the stool shipment. Released placebo units are affixed with the same label as active FMP250 units, though the specialized lot numbers will allow for differentiation.

[figure not shown]

NOW® Foods brands each Psyllium Husk Powder, Organic plastic bottle with the following label. The label provides nutritional facts, suggested usage, ingredients, and a bar code for commercial use in addition to other details. The lot number and the expiration date are printed at the bottom of each individual unit (not pictured below).

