bank where donors who provide stool for FMT undergo regular stool, blood, and nasal screenings for many different infectious agents, including SARS-CoV-2, the virus that causes the illness called COVID-19. However, not all infectious agents are screened for and some infectious agents are as yet undiscovered. Each FMT unit is only made available for use when these screens do not detect the infectious agents for which we test. Donors also undergo regular in-person clinical assessments for any risk factors, including risk factors associated with carrying SARS-CoV-2, such as visiting certain healthcare facilities, or other behaviors that may increase the risk of exposure. However, because COVID-19 is so widespread, donors may be exposed or infected without having an identified risk factor for exposure. They may also have no symptoms of infection. OpenBiome continually updates its screening guidelines and procedures as additional data, tests, and information become available. If the FMT that you receive was made from stool donated after December 1st, 2019, the stool donor was tested for the presence of SARS-CoV-2 using a nasopharyngeal swab to conduct a viral RNA test. This kind of test looks for the specific genetic material that makes up the virus. If a donor tests positive for SARS-CoV-2, OpenBiome destroys any FMT units made from that donor in the 4 weeks (28 days) before their positive test result. The donor is also disqualified from providing stool donations for at least 8 weeks. To be re-instated in the stool donation program after 8 weeks, the donor must pass all screens. Although we cannot be absolutely certain, it is unlikely that SARS-CoV-2 is present in stool donations that were provided to OpenBiome on or prior to December 1st, 2019. For this reason, testing on donors prior to December 1st has not been performed. Though these precautions are taken to minimize the risk of SARS-CoV-2 transmission via FMT, the scientific and clinical community continues to learn more about SARS-CoV-2 and COVID-19. There are limits to the detection levels of laboratory tests, including those for SARS-CoV-2. Even with current screening and testing strategies, there may be additional risks that are unknown at this time. Although the donor screening tests we perform are likely to prevent you from receiving FMT from a donor who is infected with SARS-CoV-2, we cannot be absolutely certain that the stool you receive has not been contaminated with the SARS-CoV-2 virus.

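### Exploratory engraftment analysis: recipients who share a stool donor are treated as independent, and the Random Forest has no stated validation unit

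*Combined protocol and SAP*

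**What the plan says.** Section 9.2.1.1 sets out the engraftment analysis. The test is given as "Wilcoxon signed-rank (paired) statistical tests will be used to evaluate the level of microbial similarity (Bray-curtis) between donor, pre-FMT and post-FMT". The prediction step reads "Machine learning models, Random Forest procedure, will be fitted in R-studio to predict bacterial engraftment and their persistence, as previously described". Neither sentence mentions a donor cluster, and the second gives no hold-out or resampling unit.

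Other sections describe the product:

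- Section 3.2 explains a comparison by "considering that we will utilize single donor FMP250 samples", so each active unit has one donor.
- Section 7.4.4 says of the label: "The lot number is formatted as XXXX-YYYY-ZZ, where XXXX is the donor number, YYYY is the donation number, and ZZ marks the bottle number". One donor can therefore give several donations, and one donation several bottles.
- Section 13.1.1, on a donor who tests positive for SARS-CoV-2, says "OpenBiome destroys any FMT units made from that donor in the 4 weeks (28 days) before their positive test result", again several units per donor.
- Section 7.1.1 contracts the supplier to "supply 135 investigational FMP250 and 135 Placebo FMP250".

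Section 12.3 has no stratification factors. The logistic model in section 12.1 adjusts for subject characteristics at baseline. Section 12.4.3 lists microbial profiles as exploratory.

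**The concern.** Each recipient's stool is compared with that of his or her own donor. Recipients of one donor share the reference profile and whatever makes that donor's bacteria easy or hard to transfer, so their changes in similarity may be correlated. A signed-rank test over recipients counts each as a separate piece of evidence. If a handful of donors stand behind 90 recipients, the evidence about FMP250 as a product is thinner than the count suggests.

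The Random Forest raises a related question. If validation splits by subject, recipients of one donor can sit on both sides of the split. The model can then gain accuracy by recognising the donor, and that gain would not carry over to a new donor.

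Engraftment is part of the trial's hypothesis in section 3.1, so it is worth knowing whether a positive finding describes FMP250 or only the donors who happened to supply it.

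**Working it through.** **The plan's own figure.** The documents give no sample size, power or error rate for engraftment. The only related figure is about 80% power for the primary comparison (section 12.1: 45 per arm, 55% vs 27%, two-sided 0.05). It reproduces. The mean rate is 0.41, the pooled standard error √(2 × 0.41 × 0.59 / 45) = 0.1037, and the unpooled one √((0.55 × 0.45 + 0.27 × 0.73) / 45) = 0.0994. Then (0.28 − 1.96 × 0.1037) / 0.0994 = 0.77, a power of 0.78. The donor question does not bear on it.

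**Inputs.** Active recipients at day 0: 2 arms × 45 = 90. The other 45 of the 135 active units go to the placebo arm at week 8. The number of donors K and the ICC are not in the documents; both are assumed here, with equal donor groups and normally distributed changes.

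**Formula.** With m = n / K recipients per donor, the design effect is D = 1 + (m − 1) × ICC. The true two-sided error of a nominal 5% test is about 2 × [1 − Φ(1.96 / √D)]. The null here is zero mean change averaged over donors.

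**Example.** 90 recipients, 6 donors, ICC 0.20: m = 15, D = 1 + 14 × 0.20 = 3.8, 1.96 / √3.8 = 1.005, error 0.315. The effective sample size is 90 / 3.8 = 24.

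| Recipients | Donors | ICC 0.05 | ICC 0.10 | ICC 0.20 |
|---|---|---|---|---|
| 90 pooled | 6 | 0.133 | 0.206 | 0.315 |
| 90 pooled | 9 | 0.104 | 0.155 | 0.241 |
| 90 pooled | 15 | 0.080 | 0.110 | 0.166 |
| 90 pooled | 30 | 0.062 | 0.074 | 0.098 |
| 45, one arm | 6 | 0.089 | 0.127 | 0.196 |
| 45, one arm | 9 | 0.074 | 0.098 | 0.144 |
| 45, one arm | 15 | 0.062 | 0.074 | 0.098 |
| 45, one arm | 30 | 0.053 | 0.056 | 0.062 |

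Simulating the signed-rank test itself agrees to about one percentage point. For example, with 9 donors and 90 recipients it rejects in 10.0%, 14.9% and 23.5% of runs at the three ICC values. With no sharing, or an ICC of zero, it rejects in about 5%. A t-test on donor means stayed at 4.7% to 5.1% in the settings checked.

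**A different null.** If the null is no change in any recipient (pre and post exchangeable), simulated Bray-Curtis values gave rejection rates of 4.9%, 5.8%, 5.1% and 4.3% with 1, 5, 9 and 90 donors. There is no inflation, even with one donor for everyone.

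**Random Forest.** In simulations whose features carried only a donor fingerprint (5 or 9 donors), the cross-validated AUC was:

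| Latent donor ICC | Split by subject | Whole donors held out |
|---|---|---|
| 0 | 0.49 to 0.51 | 0.49 to 0.52 |
| 0.10 | 0.55 to 0.57 | 0.50 |
| 0.23 | 0.65 to 0.66 | 0.49 to 0.54 |

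**The case against.** The strongest reply is that the documents state none of the conditions for inflation. The label format is the supplier's general one and does not show how units reach subjects here; shared donors are a likely inference. The donor ICC is unknown. For the narrow null of no change in any recipient, the named test is sound. All this stands, so the point has to be conditional. That narrow null, however, cannot support a statement about FMP250 from donors outside the trial.

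A reader might also infer any of the following, which the documents do not support:

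- *The Random Forest is validated wrongly.* Section 9.2.1.1 gives no scheme and refers to previous work. The gap is silence.
- *Donor is ignored throughout.* Section 9.2.1.1 compares recipients with donors and removes strains common to the donor and pre-treatment samples. What is missing is donor as a cluster.
- *The site cannot link donor to subject.* The pictured FMP250 log in section 7.3 has no subject column, but it is an example of a supplier form that goes back to the supplier. Another site record may hold the link, and the donor comparison could not be run without one.
- *The fibre question is compromised.* That question is a between-arm contrast. If donors are spread over both FMT arms, it is not invalidated, for engraftment or for clinical response.

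Pooling is a further assumption: the plan does not say that the two FMT arms are tested together, and the error is smaller for one arm of 45.

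**Conclusion.** The concern holds as a conditional one, confined to an exploratory analysis. The plan does not say how many donors are used or how shared donors are handled. If donors are shared and engraftment differs by donor, the recipient-level pre/post p-values are too small for conclusions beyond the donors used. The true error of the nominal 5% test is then about 6% to 32% for 90 pooled recipients and about 5% to 20% for one arm of 45, on the assumed 6 to 30 equal donor groups and ICC of 0.05 to 0.20. With many donors and a low ICC the effect is negligible. Subject-level validation of the Random Forest could also reward donor recognition, modestly at an ICC of 0.10 and more clearly at 0.23.

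A reader might take this to mean that the engraftment p-values are wrong as they stand, or that the primary result is at risk. Neither follows. The first depends on facts the documents do not give, and the primary chi-square comparison is not invalidated. This is a cheap improvement to the plan.

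**What to change.** 1. Link the donor number on the lot label to each subject in a restricted, unblinded site record. Do not add subject IDs to the log returned to the supplier: section 7.4.4 says lot numbers distinguish active from placebo units, so that form would set allocation beside identity and send it off site.
2. Report the number of donors and the recipients per donor, by arm.
3. In section 9.2.1.1, keep the signed-rank test and add an analysis with donor as the cluster: a t-test on donor means, or a mixed model with a donor random intercept. If donors are very few, limit conclusions to the donors used.
4. State that the Random Forest is validated by leaving out whole donors.

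The clinical response model needs no donor term on this account.

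The cost is analysis wording and one site record, with no extra subjects, samples or visits. Intervals will be wider and power low if donors are few, and a donor random intercept is poorly estimated in that case. A sign-flip test by donor has a smallest two-sided p of 2 / 2^K. That is 2/64 = 0.031 with six donors but 2/32 = 0.0625 with five, so it cannot reach 0.05 with five or fewer.

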9.2.2 Special Correlative Study #2

9.2.2.1 Assessment

Lamina propria mononuclear cells (LPMCs) are the key effectors within the mucosa. Numerous studies have characterized the contribution of bacterial signals to the effector functions of LPMCs, but the signatures associated with prebiotic supplementation are

limited. To characterize these profiles as we have done previously, LPMCs will be purified from digested endoscopic biopsy tissue and cryopreserved. We have optimized processing and freezing conditions to allow for efficient recovery and immune phenotyping by flow cytometry. These samples will then be used to phenotype innate and adaptive lymphocyte effector cell function. In addition, to profiling CD4+ T cell subsets by transcription factor (RORyt, T-bet, GATA-3, FoxP3) and intracellular cytokine production (IFN γ , IL-4, IL-17, IL-22), CD8+ T cells from the lamina propria and intraepithelial lymphocyte fraction will be profiled.

10. Measurement of Effect

10.1 Response Criteria

10.1.1 Primary Endpoint Assessments

10.1.1.1 Mayo Scoring System³⁰

The Mayo Scoring System will be used for the assessment of ulcerative colitis activity. It is a composite score that ranges from 0-12 based on the following four categories: bleeding, stool frequency, physician assessment, and endoscopic findings. A partial Mayo Score ranges from 0-9 and can also be utilized if no endoscopic visualization is available to assess disease activity.

Study subjects will be evaluated by a full Mayo score at day 0 and week 8, and a partial Mayo score at the week 4 clinic visit. Both clinical response and remission will be evaluated at week 8 post-FMT. Clinical response is described as a reduction of the Mayo score by >3 points and >30% reduction from baseline with an accompanying decrease in the sub-score for rectal bleeding of at least 1 point. Clinical remission will be defined by Mayo score \leq 2 without any sub-score >1, and Mayo endoscopic sub-score 0-1.

Table 2. Mayo Scoring System for the assessment of ulcerative colitis activity.

Stool frequency [†]
0 = Normal no. of stools for this patient
1 = 1 to 2 stools more than normal
2 = 3 to 4 stools more than normal
3 = 5 or more stools more than normal
Subscore, 0 to 3
Rectal bleeding [‡]
0 = No blood seen
1 = Streaks of blood with stool less than half the time
2 = Obvious blood with stool most of the time
3 = Blood alone passes
Subscore, 0 to 3
Findings on endoscopy
0 = Normal or inactive disease
1 = Mild disease (erythema, decreased vascular pattern, mild friability)
2 = Moderate disease (marked erythema, lack of vascular pattern, friability, erosions)
3 = Severe disease (spontaneous bleeding, ulceration)
Subscore, 0 to 3
Physician's global assessment [§]
0 = Normal
1 = Mild disease
2 = Moderate disease
3 = Severe disease
Subscore, 0 to 3

* The Mayo score ranges from 0 to 12, with higher scores indicating more severe disease. Data are from Schroeder et al.²⁴

† Each patient serves as his or her own control to establish the degree of abnormality of the stool frequency.

‡ The daily bleeding score represents the most severe bleeding of the day.

§ The physician's global assessment acknowledges the three other criteria, the patient's daily recollection of abdominal discomfort and general sense of well-being, and other observations, such as physical findings and the patient's performance status.

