4.2 Inclusion Criteria

1. Male or Female \geq 18 years of age.
2. Documentation of prior history of mild to moderate UC.
3. Endoscopy confirmed active UC \geq 15 centimeters at day 0 screening colonoscopy.

- a. As defined by a total Mayo scoring of 4-10 with an endoscopic sub-score ≥ 1 and a stool frequency or rectal bleeding sub-score of ≥ 1 .
4. Patients must have a descending intact colon.
5. Patients taking steroid or biologic therapy must be on a stable dose for 4 weeks prior to screening and maintained throughout the trial.
6. Eligible patients willing to undergo serological and fecal screening testing prior to FMT to document baseline status:
 - a. Urine Testing
 - i. Pregnancy test (women with childbearing potential)
 - b. Blood Testing
 - i. B-HCG (research purposes)
 - ii. CBC, ESR, CRP, and BMP (standard of care)
 - iii. HIV, type I and II (standard of care)
 - iv. Hepatitis A B C Profile (standard of care)
 - v. RPR (*treponema pallidum*) (research purposes)
 - vi. CMV IgM (standard of care)
 - vii. Quantiferon-TB (standard of care)
 - c. Stool Testing
 - i. Calprotectin (standard of care)
 - ii. Clostridium Difficile Toxin PCR (standard of care)
 - iii. Ova & parasites (standard of care)
 - iv. Gastrointestinal Pathogen PCR Panel (standard of care)
 1. *Campylobacter* species
 2. *Plesiomonas Shigelloides*
 3. *Salmonella* Species
 4. *Vibrio* Species
 5. *Vibrio cholerae*
 6. *Yersinia Enterocolitica*
 7. Enterotoaggregative *E. coli* (EAEC)
 8. Enteropathogenic *E. coli* (EPEC)
 9. Enterotoxigenic *E. coli* (LT/ST)
 10. Shigalike toxin producing *E.coli* I (STX/ST2)
 11. *Cryptosporidium*
 12. *Cyclospora cayetanensis*
 13. *Entamoeba cayetanensis*
 14. *Giardia*
 15. *Adenovirus* F 40/41
 16. *Astrovirus*
 17. *Norovirus* GI/GII
 18. *Rotavirus* A
 19. *Sapovirus*
 20. *GID* PCR INTERP

7. Patients must discontinue anti-rCDI antibiotics (e.g. vancomycin, fidaxomicin) 48 hours prior to FMT delivery procedure.

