6.1.1 Screening Visit (Days -28 to -3)

- Informed consent
- Medical history
- Medication history
- Physical exam
- Blood Testing
 1. B-HCG (research purposes)
 2. CBC, ESR, CRP, and CMP (standard of care) *
 3. HIV, type I and II (standard of care) *
 4. Hepatitis A B C Profile (standard of care) *
 5. RPR (treponema pallidum) (research purposes)
 6. CMV IgM (standard of care) *
 7. Quantiferon-TB Gold Plus, 1 Tube (standard of care) *
- Stool Testing
 1. Calprotectin (standard of care) *
 2. Clostridium Difficile Toxin PCR (standard of care) *
 3. Ova & parasites (standard of care) *
 4. Gastrointestinal Pathogen PCR Panel (standard of care) *
 - *Campylobacter* species
 - *Plesiomonas Shigelloides*
 - *Salmonella* Species
 - *Vibrio* Species
 - *Vibrio cholerae*
 - *Yersinia Enterocolitica*
 - Enteroaggregative *E. coli* (EAEC)
 - Enteropathogenic *E. coli* (EPEC)
 - Enterotoxigenic *E. coli* (LT/ST)
 - Shigalike toxin producing *E.coli* I (STX/ST2)
 - *Cryptosporidium*
 - *Cyclospora cayetanensis*
 - *Entamoeba Cayetanensis*
 - *Giardia*
 - *Adenovirus F 40/41*
 - *Astrovirus*
 - *Norovirus GI/GII*
 - *Rotavirus A*
 - *Sapovirus*

- GID PCR INTERP
- Treatment Randomization (blinded to clinician and subject)
 1. Fiber treatment groups must receive psyllium dietary supplements (2 teaspoons/day) to begin on day -3
- Diet Recall with Clinical Nutritionist/Registered Dietician or study MD
 1. A subjective dietary record will be assessed anytime during the screening period (day -28 to -3), either by an clinic or phone call consult, in conjunction with the registered dietitian (RD). This meeting will aim to capture detailed information about food and beverages consumed over a certain (typical) period of time as an estimate of usual intake. The discussion may begin with the RD asking the subject "Could you please walk me through a typical day in terms of what you eat and drink from the time you wake up until you go to sleep?" The RD may then assess what the subject normally eats on a regular weekday, and give them the opportunity to tell them a few different options they might have for breakfast, lunch and dinner as well as snacks (if their days vary). They may also review what kinds of fruits and vegetables they consume most commonly, as well as get a sense of how much added sugar is likely in the subject's diet.
- Stool and blood samples taken for research purposes

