 - This can be collected anytime during the screening period or on the day of the screening colonoscopy, prior to blinded FMT treatment, but if the subject is randomized to receive psyllium fiber, then this should be collected before day -3 when they begin the fiber supplementation.

*: These standard of care laboratory tests must be done during the screening period. However, if the subject consents on page 5 of the informed consent form then recent laboratory results may instead be used if the subject had them conducted as standard of care within 2 weeks of signing consent.

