6.1.2 Treatment Phase

Eligible subjects will be randomly assigned to one of the three (Placebo or Investigational FMP250 +/- Psyllium) treatment groups. A series of randomized blocks of fixed size will be generated with a 1:1:1 allocation ratio. This will provide assurance that after a given block has completed subject enrollment, there will be the same number of subjects assigned to each of the three study arms.

Treatment assignment will be done during the screening visit because participants randomized to receive fiber supplementation must be provided two psyllium bottles to begin consumption 3 days prior the colonoscopy.

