7.1.2 Psyllium Husk Powder

All subjects assigned to the fiber treatment arms will be required to take 1 teaspoon (approximately 5 grams) of psyllium husk powder twice a day (morning and night) for 8 weeks, beginning 3 days prior to Week 0 screening colonoscopy. To simplify, enrolled participants will consume approximately 10g of psyllium per day for 59 days.

The FDA characterizes psyllium seed husk as the dried form of a psyllium seed coat³³.

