7.8.2 Psyllium

Subjects randomized into the psyllium fiber treatment group will receive two bottles of the *Psyllium Husk Powder, Organic* product to begin consuming three days prior to the day 0 colonoscopy. They will be asked to take one teaspoon (approximately 5 grams) of this fiber supplement twice a day until their week 8 clinic visit which will be approximately 59 days. The twice a day dosage is advised to be taken once in the morning (e.g. breakfast) and once in the night (e.g. dinner) to help with subject compliance.

NOW® Foods recommends a tablespoon of this product to be mixed in at least a cup of liquid to avoid the risk of choking.

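### The only Mayo score scheduled before FMT is on day 0, so the primary baseline follows about three days of psyllium in FMT+fibre and none in FMT alone

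*Combined protocol and SAP*

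**What the plan says.** **Assignment.** Section 6.1.2: "Treatment assignment will be done during the screening visit".

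**Psyllium start.** Section 6.1.1: "Fiber treatment groups must receive psyllium dietary supplements (2 teaspoons/day) to begin on day -3". Section 7.1.2 has it "beginning 3 days prior to Week 0 screening colonoscopy", Section 7.8.2 tells subjects "to begin consuming three days prior to the day 0 colonoscopy", and Section 7.10 agrees. In the text available to us, the psyllium row of Table 1 (Section 6.1) appears to begin in the day-0 column. That may be a fault of text extraction, but table and text should be reconciled.

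**Mayo scores.** Section 10.1.1.1: "Study subjects will be evaluated by a full Mayo score at day 0 and week 8". It adds a partial score at week 4. Neither the screening list in Section 6.1.1 nor Table 1 contains a Mayo score, and Section 6.1.2.1 labels day 0 as baseline. Eligibility is judged on the same day-0 score (Section 4.2: "As defined by a total Mayo scoring of 4-10 with an endoscopic sub-score").

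**Endpoint and contrast.** Response at week 8 needs a fall of more than 3 points and more than 30% from baseline, with a rectal-bleeding fall of at least 1 (Sections 10.1.1.1 and 12.4.1). Section 12.1 compares FMT+psyllium with FMT alone by chi-square.

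**A precaution taken elsewhere.** For research stool and blood, Section 6.1.1 says that "if the subject is randomized to receive psyllium fiber, then this should be collected before day -3 when they begin the fiber supplementation".

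**The concern.** A change-from-baseline endpoint in a randomised comparison needs a baseline that treatment has not touched. Here the symptom part of the baseline can be touched in one arm of the primary contrast only.

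The protocol supplies a mechanism: Section 2.4.2 expects psyllium to firm stool and reduce bowel movements in diarrhoea, and stool frequency is one of the four Mayo sub-scores. If psyllium lowers the day-0 score, response becomes harder to reach in the fibre arm alone, and the plausible cost is lost power for FMT+fibre. If early psyllium instead worsened symptoms, the bias would favour fibre.

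The rule for research samples shows that the run-in was recognised as a threat to pre-treatment measurements. The primary endpoint has no matching protection.

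**Working it through.** **1. Length of the run-in.** Sections 7.1.2 and 7.8.2 give about 59 days of psyllium. Eight weeks is 56 days, and 59 - 56 = 3 days before day 0.

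**2. What one point does to the response rule.** On an integer scale, more than 3 points means at least 4. For entry scores 4 to 10 the 30% condition never binds, since even at 10 a fall of 4 is 40%. A subject going from 8 to 4 responds if bleeding also falls by 1. The same subject read as 7 on day 0 has a fall of 3 and does not respond. A fibre subject whose score drops one point before day 0 therefore needs a 5-point fall from the pre-treatment level, against 4 in FMT alone.

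**3. The plan's power.** Inputs from Section 12.1: p1 = 0.55, p2 = 0.27, n = 45 per arm, two-sided alpha 0.05. With p̄ = 0.41:

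- null SE = √(2 × 0.41 × 0.59 / 45) = 0.1037
- alternative SE = √((0.55 × 0.45 + 0.27 × 0.73) / 45) = 0.0994
- power = Φ((0.28 - 1.96 × 0.1037) / 0.0994) = Φ(0.77) = 0.780

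This fits the stated figure of approximately 80%.

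**4. Cost of a lower observed fibre-arm rate.** Same formula, FMT alone held at 27%:

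| Observed fibre-arm response | Power |
|---|---|
| 55% | 0.780 |
| 54% | 0.750 |
| 53% | 0.718 |
| 52% | 0.685 |
| 50% | 0.614 |
| 45% | 0.427 |

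Each point lost costs about 3 points of power near the planned rate. This is a sensitivity range, not an estimate. The documents give no figure for how many points, if any, would be lost.

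**5. Could the planned baseline check reveal a shift?** Section 12.1 compares the groups at baseline on the primary criteria. Assignment precedes psyllium, so pre-psyllium scores are equal in expectation and a day-0 difference estimates the shift, apart from any selection on day 0. Half of Group 3 also takes psyllium (Section 3.1), and no FMT has yet been given. Fibre and no-fibre subjects can therefore be pooled: 45 + 45/2, about 67 on each side. The sub-score SD is not in the documents; 0.8 to 1.0 is assumed. Power ≈ Φ(shift / (SD × √(2/67)) - 1.96):

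| Mean shift (points) | SD 1.0 | SD 0.8 |
|---|---|---|
| 0.5 | 0.82 | 0.95 |
| 0.25 | 0.30 | 0.44 |
| 0.1 | about 0.1 | about 0.1 |

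With the two primary arms alone (45 against 45), a 0.5-point shift gives Φ(0.5 / (1.0 × 0.2108) - 1.96) = Φ(0.41) = 0.66 at SD 1.0 and Φ(1.00) = 0.84 at SD 0.8. The pooled comparison is better, but Section 12.1 does not name it.

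**6. Could the planned adjustment correct a shift?** No. The logistic model in Section 12.1 would take the day-0 score as covariate, and that is the affected value. The outcome would still be defined as a fall from it. Correcting individual subjects needs a score taken before psyllium.

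**The case against.** The other side has good points, and most of them limit the claim.

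- **A shift can be checked.** A reader might infer that a baseline shift could never be detected. The documents do not support that: randomisation precedes psyllium, and a comparison of day-0 scores is planned. Step 5 shows that a large mean shift would probably be seen. What is lost is sensitivity to small shifts and any correction for individual subjects.
- **The direction is not established.** A reader might infer that the fibre arm is biased downwards. Section 2.4.2 also says psyllium can soften stool or increase bowel movements in constipation. Sections 2.5.1.2 and 13.1.7 list possible bloating and, rarely in older subjects, cramps and discomfort, which could raise the physician's global assessment. Sections 2.5.2.2 and 3.2 describe the evidence for fibre alone in UC as inconsistent or not significant.
- **The effect may be blurred.** No recall window is given for stool frequency or bleeding, so some recalled days may precede psyllium. Bowel preparation (Section 7.8.1) disturbs stool counts in every arm.
- **Day 0 is a defensible baseline.** It is contemporaneous with endoscopy and immediately precedes FMT, and the stated aim is whether fibre enhances FMT. If psyllium does lower the score, this choice works against fibre and does not produce a false claim for it.

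The timing asymmetry itself stands, as does the absence of any pre-psyllium Mayo score.

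**Conclusion.** The concern holds in a limited form and should be fixed. It is clear from the text sections that the primary baseline is scored after about three days of assigned treatment in one arm of the primary contrast and not in the other; the Table 1 row still has to be reconciled with them. Size and net direction are unknown. A lower fibre-arm baseline and some loss of power are plausible, at about 3 points of power per point of response lost, starting from 78%. That figure rests on the plan's own rates and on FMT alone staying at 27%.

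The planned baseline comparison gives partial protection, under an assumed SD of 0.8 to 1.0: good for a mean shift of half a point, poor for a quarter point or less. The planned covariate adjustment gives no correction.

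A reader might also fold in the replacement of randomised but untreated subjects (Section 8.2) and the treated-only response set (Section 12.6.2). Those concern exclusions after randomisation. They are a separate issue and do not strengthen this one.

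**What to change.** 1. In Sections 6.1.1 and 10.1.1.1 and in Table 1, add a partial Mayo score (stool frequency, rectal bleeding, physician's global assessment) for all subjects at the screening visit, before randomisation and any psyllium. The instrument is already provided for in Section 10.1.1.1: "A partial Mayo Score ranges from 0-9 and can also be utilized if no endoscopic visualization is available to assess disease activity".
2. In Section 12.1, keep the day-0 baseline as primary. Pre-specify a sensitivity analysis of week-8 response whose baseline, in all arms, combines the screening sub-scores with the day-0 endoscopic sub-score.
3. Report day-0 sub-scores by fibre versus no fibre, pooling across FMT assignment.
4. Reconcile the psyllium row of Table 1 with the text.

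**Cost.** Three sub-scores at a visit that already includes a physical examination, one added analysis and one table. The screening symptom scores can be up to about four weeks older than the endoscopy, equally in all arms, and the physician's assessment would be made without that day's endoscopy. The sensitivity baseline also counts stool bulking by psyllium as response, which is a reason to keep it as a sensitivity analysis. Treatment and eligibility do not change. The score has to be added before subjects are enrolled, because it cannot be collected afterwards.
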